2.2 Rationale

GTx-024 has been evaluated in 21 completed and ongoing clinical studies enrolling over 1,500 total subjects. GTx-024 has been generally well-tolerated, including single doses up to 100 mg and multiple doses up to 30 mg once daily for up to 14 days. In longer studies, GTx-024 has also been generally well-tolerated, including 1, 3, and 9 mg daily doses for up to 184 days.

Previous clinical studies demonstrated that daily doses up to 30 mg of GTx-024 were well-tolerated in healthy male volunteers. Both 10 mg and 30 mg daily doses were evaluated in Protocol G100402 for up to 14 days. Elevated alanine transaminase (ALT) (any elevation outside the upper limit of the normal range [ULN]) was the most common adverse event (AE) experienced. None of the subjects in the 10 mg dose

Compound No.: GTx-024 Author: [name]

group were discontinued from the study due to ALT elevations. Six out of 71 subjects experienced ALT increases above two times the ULN.

GTx-024 3 mg given daily was evaluated in two completed Phase 3 trials, in over 600 subjects, for the prevention and treatment of muscle wasting (cachexia) in subjects with advanced non-small cell lung cancer receiving chemotherapy. GTx-024 3 mg increased LBM in both studies and was safe and well-tolerated. Subjects in the GTx-024 and placebo groups experienced similar AEs, and these AEs were consistent with the background chemotherapy regimen.

Although GTx-024 3 mg was chosen for its anabolic activity in muscle for the completed Phase 3 program, a dose of 9 mg once daily was selected for hormonal therapy in the ongoing Phase 2 trial in ER+/AR+ metastatic BC in order to achieve a higher exposure that is both safe and more likely to be efficacious in women with advanced BC. Seven out of twenty-two subjects with advanced, heavily pretreated (hormonal therapy, radiation, and chemotherapy) BC demonstrated clinical benefit (CB) (stable disease [SD]) at 6 months. In one subject with SD (by Response Evaluation Criteria in Solid Tumors [RECIST], Version 1.1²), tumor regression of 27% in a single target lesion was demonstrated. Consistent with the previous studies, GTx-024 remained safe and well-tolerated.

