4 STUDY DESIGN

This is an open label, multicenter, multinational, randomized, parallel design Phase 2 study to assess the efficacy and safety of GTx-024 in postmenopausal subjects with ER+/AR+ BC. Subjects will be randomized to receive either GTx-024 9 mg or 18 mg given PO daily for up to 24 months. Each dose arm will be treated independently and each assessed for efficacy using Simon's two-stage (optimal) design¹. Subjects will be randomized in a 1:1 fashion to one of the two dose arms. Randomization will be stratified by subjects presenting with bone only metastases and all other subjects, and further by setting of immediately preceding therapy (adjuvant setting or metastatic setting) in order to balance the proportion of subjects with these presenting features in each dose arm. There is no intent to statistically compare the two dose arms, but to determine whether either or both doses result in an acceptable CBR, defined as the proportion of evaluable subjects (i.e., subjects with centrally confirmed AR+ and who receive at least one dose of study drug) with either CR, PR, or SD by RECIST 1.1 at week 24, consistent with 30% while maintaining an acceptable safety profile. Given such a result, future exploration of GTx-024 in ER+/AR+ BC would be warranted at that dose level.

Thirty-six to 88 (36–88) subjects with centrally confirmed AR+ who receive at least one dose of study drug (evaluable subjects) will be needed for primary efficacy analysis purposes and will be a subset of the FAS. Thirty-six to one hundred and eighteen (36–118) subjects, including replacement subjects, will be randomized in a 1:1 fashion to receive a daily PO dose of either GTx-024 9 mg or 18 mg. Thirty of the aforementioned subjects may be considered replacement subjects to account for lack of centrally confirmed AR+ status or for the rare subject who is randomized but does not receive study drug (assumes 25% of enrolled subjects are not evaluable for the primary efficacy analysis). Other statistical parameters that are part of the sample size calculation are α = 0.025 (one-sided) and power = 90%. The first stage in each study arm will be assessed among the first 18 evaluable subjects. If at least 3/18 subjects achieve CB (defined as CR, PR, or SD) at week 24, the arm will proceed to the second stage of recruitment up to a total of 44 evaluable subjects per arm. Otherwise, the arm will be discontinued for lack of efficacy. Statistical significance, i.e., rejection of

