7.3 Treatment Phase

The first dose of study drug will be administered on the day of randomization (Visit 2). GTx-024 will be administered daily for up to 24 months from randomization or until disease progression (whichever is sooner), subject's withdrawal of consent, or intolerability.

During the study treatment phase, the subjects will be scheduled for a visit every 6 weeks. Visit 7 at week 28 will only take place in subjects who have CR or PR at Visit 6 (week 24; see below).

The following tests and procedures will be performed during Visits 3, 4, 5, and 6 (weeks 6, 12, 18, and 24) in the treatment phase:

Review concomitant medications

Compound No.: GTx-024 Author: [name]

- Physical examination, including weight and vital signs (heart rate, respiratory rate, body temperature, blood pressure in a sitting position)
- ECOG performance status
- Blood sampling for: hematology, biochemistry, serum lipid profile, coagulation status, serum hormones, and PSA
- Urine analysis, if clinically indicated
- AE collection
- Subjects will be asked to complete a QoL questionnaire (EQ-5D-5L)
- GTx-024 drug accountability/dispensation

Radiologic assessments for anti-tumor effect will be done every 12 weeks whilst subjects receive treatment (Visits 4, 6, and thereafter). The same imaging technique must be used throughout the study in a given subject. Bone scans will be performed at screening and then every 12 weeks whilst subjects receive treatment (Visits 4, 6, and thereafter) in only those subjects with baseline bone metastases, or if clinically indicated. In addition, if any subject has CR or PR at Visit 6 (week 24), in compliance with RECIST 1.1 guidelines, a confirmation of the CR or PR (CT/MRI/bone scan) should be done 4 weeks later (Visit 7; week 28). The central imaging facility will also perform tumor volumetric assessment for the subjects undergoing CT scanning during Visits 4 and 6 (weeks 12 and 24). Blood sampling for CTC enumeration will be done at the same visits as the radiological assessments during the treatment phase; i.e., every 12 weeks whilst subjects receive treatment (Visits 4 and 6), but not at the confirmation of the CR or PR visit (Visit 7; week 28) or at Visits 8–13.

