8.1 Clinical Evaluations

All treatment decisions will be based on Investigator assessments, including determination of PD.

Imaging Assessments:

CT with contrast of the chest, abdomen, and pelvis including the liver and the adrenals will be performed to assess tumor status. If contrast is contraindicated, CT without contrast for chest and pelvis and MRI of the abdomen should be performed. Whichever imaging method is selected should be used for all study assessments in a given subject.

Bone scintigraphy (bone scans) will be performed to assess bone metastases. Bone scans will be performed at screening and then every 12 weeks whilst subjects receive treatment (Visits 4, 6, and thereafter) in only those subjects with baseline bone metastases, or if clinically indicated.

Tumor lesions will be assessed using RECIST 1.1 at the site based on the local reading facility. Scans will be sent to the central imaging facility, blinded to the GTx-024 dose, for final efficacy outcomes analysis.

In compliance with RECIST 1.1, if any subject has CR or PR at Visit 6 (week 24), a confirmation of the CR or PR (CT/MRI/bone scan) should be done 4 weeks later (Visit 7; week 28).

Tumor volumetrics will be performed by the assigned central vendor only for subjects who have CT scans at screening and then at weeks 12 and 24 (Visits 4 and 6). Tumor volumetrics will be performed by an independent 3rd party vendor who is masked to individual subject treatment and outcomes.

Compound No.: GTx-024 Author: [name]

Medical History and Medication History:

The medical history of the subject will be obtained by the PI from the subject's medical record. The medical history will include a review of the hormonal status of the BC (ER, HER2).

Medication history will include all medications currently being taken (rather than the lifelong medication history) and will include both prescription and over-the-counter medicines (also including nutritional supplements or herbal treatments). This will include prior cancer treatments taken.

Demographics:

The following demographic data will be collected: age, gender, and race.

Physical Examination:

Physical examination will include organ palpation, lymph nodes palpation, skin turgor, and muscle weakness measurement.

Height and weight will also be measured as outlined in the schedule of events.

AEs will be followed-up to resolution, and while further physical examinations may take place, they will not be mandatory.

Vital Signs:

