11.2 Sample Size Considerations

Based on the above assumptions, a sample size of N = 44 ER+/AR+ BC subjects with centrally confirmed AR+ status who receive at least one dose of study treatment (evaluable subjects) are needed for each arm that proceeds to the second stage. An arm will proceed to the second stage if at least 3 subjects among the first 18 evaluable subjects randomized achieve CB, defined as CR, PR, or SD as per RECIST 1.1, as determined by central review. If an arm proceeds to the second stage, a statistical success that favors further evaluation of the dose arm(s) in future trials will require at least 9/44 subjects to achieve CB at week 24, i.e., the null hypothesis of an unacceptably low rate of CB, \leq 10.0%, can be rejected in favor of the alternative hypothesis that indicates the higher rate, \geq 30.0%, is more likely. The lower limit of the exact 95% confidence interval at exactly 9 CBs, 11.0%, exceeds 10.0%¹².

Compound No.: GTx-024 Author: [name]

At any time during the first stage, if 3 evaluable subjects in any one arm achieve CB at week 24, that arm will proceed to the second stage; otherwise, it will be halted for lack of efficacy. If at any time, 9 evaluable subjects in an arm achieve CB at week 24, the efficacy criteria for that arm has been met; however, the arm should proceed to full accrual of 44 evaluable subjects in the successful arm(s) in order to better characterize the CB rate, evaluate secondary endpoints, and describe the safety profile of the dose level(s). To reiterate, the intent of the trial is not to statistically compare the CB rate between the two dose arms and the trial is not powered to do so.

Subjects whose AR+ status is not centrally confirmed will be replaced in order to accrue the necessary number of evaluable AR+ subjects to be included in the primary analysis. Subjects who are not confirmed AR+ may remain on the trial, but will not be part of the primary efficacy analysis – these subjects will contribute to secondary and tertiary analyses as noted below. Subjects who are randomized but never receive study drug will be replaced as well. Assuming that 25% of subjects enrolled are not evaluable for the primary efficacy analysis for the reasons noted above, up to 30 additional subjects may need to be randomized.

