11.4.2 Definition of analysis endpoints; primary, secondary, tertiary, exploratory, safety

Primary efficacy endpoint

Tumor response in terms of clinical benefit will be assessed by RECIST 1.1 criteria from centrally read CT scans obtained at the 24 week assessment. Tumor response is judged relative to baseline tumor assessments. An evaluable subject will be considered to have a response of CB if the assessment indicates CR, PR, or SD. The primary assessment is among evaluable subjects in the FAS at 24 weeks in each of the 9 mg and 18 mg arms. An evaluable subject who does not have a week 24 assessment for any reason remains in the evaluable subset of the FAS and is considered a failure to achieve CB (CR, PR, or SD).

Secondary efficacy endpoints

CBR in the FAS and PPS at 24 weeks in each of the 9 mg and 18 mg arms

The following secondary efficacy endpoints will be assessed among subjects in each of the 9 mg and 18 mg arms among the evaluable subjects, the FAS, and the PPS:

ORR (CR or PR assessed by RECIST 1.1 criteria) at 24 weeks

Compound No.: GTx-024 Author: [name]

- Best (confirmed) overall response rate (BOR). BOR is defined as the best observed response for each subject up to and including the EOT. Reponses of CR or PR should be confirmed by a repeat assessment at least 4 weeks later.
- PFS: PFS is defined as the time from randomization until objective tumor progression or death due to any cause. Subjects who have no PFS events will be censored at the date of the last adequate tumor assessment. If the subject has no post-baseline tumor assessments, they will be censored at the time of randomization
- TTP: TTP is defined as the time from randomization until objective tumor
 progression or death due to disease progression. Subjects who have not
 progressed will be censored at the date of the last adequate tumor assessment. If
 the subject has no post-baseline tumor assessments but is known to be alive, they
 will be censored at the time of randomization
- Duration of response: Duration of response, in responders, is defined as the period from the date of initial CR or PR until the date of disease progression or death from any cause. Only subjects with BOR of CR or PR (i.e., responders) will be included in the analysis of duration of response. Subjects with no documented progression or death after CR or PR will be censored at the last date at which they are known to have had the CR or PR

Tertiary efficacy endpoints

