11.4.3.2 Primary efficacy analysis

The primary efficacy analysis is based on rules as set forth in Simon's two stage (optimal) design as previously described, and is based on the proportion of evaluable subjects in the FAS who achieve CB at 24 weeks. At least 3/18 evaluable subjects must achieve CB in order for the arm to proceed to the second stage. If an arm proceeds to the second stage, ≥ 9/44 subjects must have CB at 24 weeks to deem the efficacy criteria to have been met in that arm. This is the minimum number of successes needed to rule out an unacceptably low, 10%, CB rate (lower limit of the 95% confidence interval). The exact 95% confidence intervals about the CBR at week 24 will be constructed.

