11.4.3.7 Missing data/Outliers/Dropout considerations

No imputation for missing data will be carried out other than to complete partial dates using standard imputation techniques as per the Contract Research Organization's standard.

No evaluable subject will have missing data for the primary efficacy analysis because subjects who have the week 24 assessment will be classified as having CB or not, and those who do not have a week 24 assessment will classified as not having CB.

Compound No.: GTx-024 Author: [name]

With regards to missing start and stop dates for AEs and medications, imputation rules will be provided in the SAP. In addition, rules to determine in which period each AE belongs for the summary tables will also be provided in the SAP.

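### Clinical benefit at week 24 is called from the week 24 scan alone, so a subject with central progression at week 12 can count as a success; the reference for progression is also left unclear

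*Combined protocol and SAP*

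**What the plan says.** Under Primary efficacy endpoint, Section 11.4.2 takes the CB call from the central reading of the week 24 scans under RECIST 1.1. The next sentence reads "Tumor response is judged relative to baseline tumor assessments". CR, PR or SD on that assessment makes the subject a CB. The only automatic failure named is a missing week 24 assessment. Section 11.4.3.7 repeats this: "subjects who have the week 24 assessment will be classified as having CB or not", and those without the assessment are failures. Section 3.2.1 (outcome measure) and Section 11.4.3.2 (primary analysis) place no condition on earlier scans.

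Scans are also taken at week 12. Section 7.3 says "Radiologic assessments for anti-tumor effect will be done every 12 weeks whilst subjects receive treatment". Section 8.1 says "All treatment decisions will be based on Investigator assessments, including determination of PD", while Sections 5.4.2 and 8.1 send the scans to a blinded central facility for the final efficacy outcomes. PFS and TTP (Sections 3.2.2 and 11.4.2) count objective RECIST 1.1 progression whenever it occurs.

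The CB count drives both decisions in each arm. Stage 1, Section 11.2: "An arm will proceed to the second stage if at least 3 subjects among the first 18 evaluable subjects randomized achieve CB". Final, Section 11.4.3.2: "≥ 9/44 subjects must have CB at 24 weeks to deem the efficacy criteria to have been met in that arm".

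**The concern.** CB at week 24 is naturally read as free of progression through week 24. The text defines it by one scan instead, and this leaves two gaps.

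First, central PD at week 12 does not block a CB success at week 24. The primary endpoint and PFS/TTP could then disagree for the same subject on the same images.

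Second, two adjacent sentences in Section 11.4.2 can point to different references for progression. One invokes RECIST 1.1 and the other names baseline. A tumour that shrinks by week 12 and then regrows could be judged differently depending on which is followed.

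The success margin is narrow: one subject turns 8/44 into 9/44. In the earlier trial all seven subjects with CB had stable disease (Sections 2.2 and 2.3.2). The line between SD and PD is therefore likely to carry much of this endpoint.

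**Working it through.** **Step 1. Can a week 12 central progressor have a week 24 scan?** Yes, by two routes.
- The investigator does not call PD. Treatment decisions are local (Section 8.1), so she stays on drug and is scanned at week 24.
- PD leads to withdrawal (Section 5.4.3), but Section 5.4.4 asks those who withdraw, for whatever reason, to keep attending planned evaluations. A week 24 scan may then still exist.

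The discussion of an enrolment pause in Section 4 treats withdrawal before week 24 as completing the assessment. It does not say that withdrawal is a CB failure.

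**Step 2. What does that scan yield?** If it still shows PD against baseline, she is a failure and no harm is done. If it no longer does, Section 11.4.2 makes her a CB, while PFS/TTP count the week 12 event if they use the central read.

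**Step 3. The reference for progression.** Take assumed target sums of 100 mm at baseline, 73 mm at week 12 and 110 mm at week 24.
- Against baseline: 110/100 = 1.10, a rise of 10%.
- Against week 12: 110/73 = 1.51, a rise of 51%.

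The call can therefore turn on the reference. The 27% fall borrows its size from Section 2.2 ("tumor regression of 27% in a single target lesion was demonstrated"). That was one lesion in one subject with SD, with no week 12 timing and no regrowth reported, so the example is hypothetical.

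**Step 4. Reproduce the design.** Inputs:
- null rate 0.10 and alternative 0.30 (Section 11.1);
- "α = 0.025 (one-sided) and power = 90" percent (Section 4);
- at least 3/18, then at least 9/44, leaving 44 − 18 = 26 subjects in stage 2.

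Pass probability at rate p:

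P(p) = Σ (x = 3 to 18) C(18,x) pˣ(1−p)¹⁸⁻ˣ × Pr[Bin(26,p) ≥ 9 − x]

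At p = 0.10 the terms for x = 3 to 9 are 0.00670, 0.00783, 0.00564, 0.00257, 0.00075, 0.00014 and 0.00002, and the rest are negligible. The sum is 0.0236, below 0.025. At p = 0.30, P = 0.904. A search over designs returns the same optimal rule. The sample size is sound.

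**Step 5. Illustration of size.** Let q be the share of evaluable subjects counted as CB despite earlier central PD. The documents give no value, so q is assumed. With a true progression-free rate of 0.10, the counted rate is 0.10 + q.

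| q | counted rate | P(pass 3/18 then 9/44) |
|---|---|---|
| 0 | 0.10 | 0.024 |
| 1% | 0.11 | 0.040 |
| 2% | 0.12 | 0.064 |
| 3% | 0.13 | 0.094 |

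**The case against.** Several points on the other side stand.

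- **The week 12 route is narrow.** It needs central PD at week 12, a week 24 scan, and a week 24 reading that no longer shows PD against baseline. Persistent growth, or a new lesion still present, remains PD. This limits frequency but does not close the gap.
- **Regrowth.** A reader might infer that the plan scores regrowth as benefit. The documents do not establish that. CB is defined by RECIST 1.1 throughout, and the baseline sentence speaks of response, for which baseline is a sensible reference. The documents do not reproduce the criteria's own reference for progression. What remains is an unreconciled pair of sentences.
- **Direction.** A reader might infer that the endpoint errs only upward. This route does, compared with a progression-free definition. But a subject with local PD and central SD at week 12 will usually stop treatment, may have no week 24 scan, and is then a CB failure. The net effect of reader disagreement is unknown.
- **Error rates.** Under the protocol's own definition of CB, the error at 10% is 0.0236. The larger figures arise only when the null rate is taken to be progression-free, with q assumed.
- **Reader for PFS/TTP.** Their definitions name none. Central reading is inferred from the general statements in Sections 5.4.2 and 8.1.

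It may also be said that the separate SAP could settle this. Section 11 leaves tests, missing data, time-to-event imputation and output specifications to it, but does not list the CB definition among them.

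**Conclusion.** The point holds as a gap in the endpoint definition. As written, central PD at week 12 does not prevent a CB success at week 24. If PFS/TTP use the central read, the same subject is also an event there. The reference for progression must be reconciled within Section 11.4.2.

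The size is unknown. The range 0.040 to 0.094, against 0.024, rests on an assumed 1 to 3 such subjects per 100 and a true progression-free rate of 10%. It should not be read as the trial's actual type I error, nor as a fault in the 3/18 and 9/44 rules, which reproduce. Nor do the documents support a claim that CBR is biased upward overall. This is a cheap improvement, worth making before central reads are used for the stage 1 decision.

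**What to change.** In Section 11.4.2, replace the baseline sentence and the CB rule with wording such as:

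*CB at week 24 requires CR, PR or SD (non-CR/non-PD for subjects with non-measurable disease only) on the central week 24 assessment and no central PD at any earlier assessment, using the same RECIST 1.1 progression definition and central read as PFS/TTP. The baseline reference applies to CR and PR only.*

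Add the no-earlier-PD condition to Sections 3.2.1 and 11.4.3.2, and name the central read in the PFS and TTP definitions so that the cross-reference works.

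The cost is a few sentences. No new scans are needed, because week 12 images are already taken and sent to the central facility. The 3/18 and 9/44 rules do not change, and treatment decisions stay as the protocol has them. The downside is that the observed CBR may be slightly lower. The change does not address local PD with central SD, where a missing week 24 scan still counts as failure; reporting the number of such subjects would show how far disagreement acts in each direction.

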3.2.2 Secondary Efficacy Outcome Measures

 Response of CB in a subject at 24 weeks regardless of central confirmation of AR status (FAS)

The following secondary efficacy outcome measures apply to both the evaluable subset of the FAS as well as to the FAS:

- OR at week 24. OR is defined as attainment of a CR or PR at 24 weeks as measured by RECIST 1.1
- BOR as measured by RECIST 1.1 and defined as: the best response recorded from the start of the study treatment until the end of treatment taking into account any requirement for confirmation. For a subject with non-measurable (non-target) disease only at baseline, SD will be defined as those with non-CR/non-PD combined response
- PFS defined as the time elapsed between randomization and tumor progression as measured by RECIST 1.1 or death due to any cause
- TTP defined as the time elapsed between randomization and tumor progression as measured by RECIST 1.1 or death due to disease progression
- Duration of response (time from documentation of tumor response to disease progression or death)

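### Read literally, the PFS censoring rule in Section 11.4.2 discards deaths that occur before any post-baseline scan, contrary to the PFS definition; the parallel TTP rule carries a vital-status condition that the PFS rule lacks

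*Combined protocol and SAP*

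**What the plan says.** Two sections define PFS, and they agree. Section 11.4.2 states: "PFS is defined as the time from randomization until objective tumor progression or death due to any cause". Section 3.2.2 likewise counts "tumor progression as measured by RECIST 1.1 or death due to any cause".

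Section 11.4.2 follows its definition with two censoring sentences. The first is "Subjects who have no PFS events will be censored at the date of the last adequate tumor assessment". The second is "If the subject has no post-baseline tumor assessments, they will be censored at the time of randomization". The second sentence places no condition on vital status.

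The next bullet defines TTP, for which only death due to progression is an event. Its corresponding sentence censors at randomization if "the subject has no post-baseline tumor assessments but is known to be alive".

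Section 7.3 schedules imaging every 12 weeks on treatment, so the first planned post-baseline scan is at week 12 (± 7 days). Sections 7.4 and 7.6 add imaging at the end-of-treatment or early termination visit, which can fall earlier. Section 11.4.3.3 estimates PFS by Kaplan-Meier, and Section 11.4.3.4 uses PFS in Cox models.

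The opening of Section 11 calls itself an overview. It leaves missing-data handling and time-to-event imputation to a separate statistical analysis plan, and no text from that plan is among the documents reviewed.

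**The concern.** A subject who dies on treatment before her first scan has a PFS event under the definition, yet she also meets the wording of the censoring sentence. If the sentence is applied as it stands, she leaves the risk set at time zero and her death is never counted.

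Such deaths would normally be known to the trial: Section 9.2.1 requires any death within 28 days of the last dose to be reported. The literal rule would therefore discard an observed event.

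The contrast with TTP sharpens the problem. The vital-status condition appears under TTP, where only some deaths are events, and is absent under PFS, where all deaths are. Two parallel rules that differ in that one phrase invite different coding.

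The arms are not compared, so PFS will be read as an absolute figure for each dose. Nothing offsets an upward shift.

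**Working it through.** **Starting point.** The plan states no figure for PFS. The only number borrowed here is 44, the evaluable sample size per arm (Section 11.2). An exact two-stage calculation with 3/18 to continue and 9/44 for success gives one-sided α = 0.0236 and power = 0.904, in line with the stated 0.025 and 90%. Neither depends on the PFS rule.

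**Step 1: the rules side by side, for a subject with no post-baseline scan.**

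| Vital status | PFS definition | PFS sentence, literal | PFS sentence, as fallback for event-free subjects | TTP as written |
|---|---|---|---|---|
| Alive | No event | Censored at randomization | Censored at randomization | Censored at randomization |
| Died of progression | Event | Censored at randomization | Event at death | Event at death |
| Died of another cause | Event | Censored at randomization | Event at death | Not an event and outside the no-scan sentence; the default of the last adequate assessment points to a screening scan, before randomization |

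The two PFS readings differ only in the death rows, and the PFS text does not choose between them. The last TTP cell is a separate gap.

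**Step 2: formula.** Let d of 44 subjects die without a scan, and let E be the number event-free at a later time t, with no other censoring before t.

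- Deaths as events: S(t) = E/44.
- Deaths censored at time 0: S(t) = E/(44 − d).
- Ratio of the second to the first: 44/(44 − d).

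Other censoring before the deaths would make this factor approximate.

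**Step 3: numbers.** The documents do not give d or the true PFS; both are assumed.

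| d | 44/(44 − d) | True PFS 55% becomes | True PFS 70% becomes |
|---|---|---|---|
| 1 | 44/43 = 1.023 | 56.3% (+1.3 points) | 71.6% (+1.6) |
| 2 | 44/42 = 1.048 | 57.6% (+2.6) | 73.3% (+3.3) |
| 4 | 44/40 = 1.100 | 60.5% (+5.5) | 77.0% (+7.0) |

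**Step 4: worked curve for d = 4.** Of the other 40 subjects, let 10 progress at week 12 (25%) and 8 of the remaining 30 at week 24 (25% is 7.5, rounded up).

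- Week 12: 30/44 = 68.2% with deaths as events; 30/40 = 75.0% with deaths censored.
- Week 24: 22/44 = 50.0% against 22/40 = 55.0%.

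In this example the curve reaches 50% at week 24 only when deaths count as events. Under the literal rule the median would be read at a later assessment.

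**Step 5: other denominators.** With 118 randomized 1:1, the full analysis set has up to 118/2 = 59 per arm, and d = 4 gives 59/55 = 1.073. In an arm closed after 18 evaluable subjects, d = 1 gives 18/17 = 1.059.

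**Step 6: scope.** The primary analysis counts a missing week 24 assessment as failure (Sections 11.4.2 and 11.4.3.7), so it does not change. The per-protocol set requires a completed week 24 evaluation (Section 11.4.1), so the case cannot arise there. That leaves PFS and the Cox models on PFS in the evaluable set and the full analysis set.

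**The case against.** The strongest reply is that the paragraph should be read in sequence. Death is an event; subjects without an event are censored at the last adequate assessment; and the no-scan sentence says what to do when such a subject has no assessment date. On that reading every early death remains an event, as both definitions require. This reading is reasonable and may well be what was meant. It does not settle the text, because the TTP bullet has the same sequence and its authors still added a vital-status condition there.

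A reader might infer that the plan intends to censor early deaths, or that reported PFS will be biased upward. The documents support neither. They show an ambiguous sentence, and the separate analysis plan, which is not available here, may resolve it.

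A reader might also take the affected group to be everyone who dies before week 12. That is too broad. The trigger is death before any post-baseline scan, and a subject who stops early may have an end-of-treatment scan first.

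On size, the objection largely stands. Eligibility requires ECOG 0 or 1 and adequate organ function, so early deaths without a scan are probably few. With one or two, the shift at 55% is 1.3 or 2.6 points. The 95% half-width at n = 44 is 1.96 × √(0.55 × 0.45/44) = 0.147, or about 15 points. The case d = 4 means 4/44 = 9% of an arm and is an upper illustration rather than a forecast.

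It is also fair that TTP is not wholly without a rule, since the default of the last adequate assessment exists. For a subject with only a screening scan, however, that default gives a date before time zero.

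**Conclusion.** The point holds as a wording defect in a secondary endpoint. Read literally, the PFS no-scan sentence contradicts the PFS definition; on the other available reading it does not; and the contrast with TTP leaves the choice to whoever programs it.

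If the literal reading were used, PFS estimates after the early deaths would be multiplied by 44/(44 − d), always in the drug's favour: 2.3% to 10.0% in relative terms for d = 1 to 4. This rests on an assumed d, a denominator of 44 and no other early censoring.

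The sample size, the error rates, the primary clinical benefit rate, the decision to continue or stop an arm and the per-protocol set are all untouched. The sentence is still worth correcting before analysis, because the error can only flatter an uncontrolled estimate and the repair is nearly free.

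**What to change.** Replace the no-scan sentences in Section 11.4.2 and carry the same wording into the separate analysis plan.

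- **PFS:** *Subjects with no post-baseline tumor assessment who have not died are censored at randomization; death before any post-baseline assessment is an event on the date of death.*
- **TTP:** *Subjects with no post-baseline assessment and no death due to disease progression are censored at randomization.*

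The cost is two sentences, with no change to sample size, data collection or trial conduct. The PFS estimate may come out slightly less favourable than under the literal rule.
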